6.1. Inclusion Criteria

Participants are eligible to be included in the study only if all of the following criteria apply. Inclusion criteria apply to Parts A and B unless otherwise noted.

1. Written informed consent from the participant has been obtained prior to any study-related procedures (as described in [Appendix 3](#)).
2. Male or female participants must be 18 to 65 years of age, inclusive, at the time of signing the informed consent.
3. Meet DSM-5 criteria ([American Psychiatric Association 2013](#)) for MDD (based on confirmation from the modified SCID), with a current major depressive episode of at least 8 weeks and not exceeding 18 months in duration at Visit 1.
4. Have a minimum score of 26 on the rater-administered MADRS at both Screening (Visit 1) and Visit 2 (Day 1 in Part A and Day –1 [Baseline] in Part B).
5. Have a CGI-S score ≥ 4 at both Screening (Visit 1) and Visit 2 (Day 1 in Part A and Day –1 [Baseline] in Part B).
6. Part A: Have a negative serum β -human chorionic gonadotropin (β -hCG) pregnancy test at Screening (Visit 1) if a WOCBP. Part B: If a WOCBP, have a negative serum β -hCG pregnancy test at Screening (Visit 1) AND a negative urine pregnancy test on Day –1 (baseline), if more than a week has passed since the serum pregnancy test at Screening. If urine pregnancy test is positive on Day –1, then a serum β -hCG pregnancy test should be done for confirmation.
7. Female participants willing to minimize the risk of becoming pregnant for the duration of the clinical study and follow-up period. A female participant is eligible to participate if she is not pregnant, not breastfeeding, and at least one of the following conditions applies:
 - a. Not a WOCBP

OR

 - b. A WOCBP who agrees to follow the contraceptive guidance in [Appendix 5](#) during the treatment period and for at least 4 to 5 weeks after the last dose of study treatment.

8. Male participants willing to minimize the risk of inducing pregnancy for the duration of the clinical study and follow-up period. A male participant must agree to use contraception as detailed in [Appendix 5](#) of this protocol during the treatment period and for at least 10 weeks after the last dose of study treatment and refrain from donating sperm during this period.
9. Able, as assessed by the investigator, and willing to follow study instructions and likely to complete all required study visits.

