7.3. Method of Treatment Assignment

All participants will be centrally assigned to randomized study treatment using an IWRS. Before the study is initiated, the log-in information and directions for the IWRS will be provided to each site.

Study treatment will be dispensed at the study visits summarized in the schedule of activities (Section 2.1 [Part A] and Section 2.2 [Part B]).

Returned study treatment should not be re-dispensed to the participants.

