4.0 INTRODUCTION

This statistical analysis plan (SAP) provides a more technical and detailed elaboration of the statistical analyses of the efficacy and safety data for part A as outlined and/or specified in the final protocol of Study 3125-104-002 and the most recent protocol amendment (Amendment 1 dated 05 March 2019; Amendment 2 dated 03 May 2019). Specifications of tables, figures, and data listings are contained in a separate document.

Part A of study 3125-104-002 is a Phase 1b, multicenter, randomized, double-blind, placebo-controlled, parallel-group (4 arms), weekly and once daily dose, 2-week study of AGN241751 in participants with major depressive disorder (MDD). The study will include a total of 7 visits and will be approximately 5 weeks in duration:

- Up to 2-week screening period
- 2-week double-blind treatment period
- 1-week safety follow-up period

After providing written consent, participants will enter a screening period of up to 14 days. Screening procedures may be conducted on up to 2 separate dates where necessary to accommodate participant and site schedule; however, every effort should be made to conduct all procedures as early as possible in the screening period, including the rater-administered montgomery- asberg depression rating scale (MADRS). Participants meeting the eligibility criteria at the end of Visit 2 (Day 1 of the randomized inpatient treatment) will be assigned a treatment and enter the double-blind treatment period.

Approximately 100 participants are planned for enrollment in the double-blind treatment period (25 participants each in the AGN-241751 and placebo groups). Participants will be randomized in a ratio of 1:1:1:1 to 1 of 4 treatment groups: 3 mg, 10 mg, and 25 mg dose AGN-241751 and placebo. All participants will be randomized to receive active treatment or placebo (Day 1, and Days 8 to 15) and placebo alone (Days 2 through 7).

[figure not shown]

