10.0 EFFICACY ANALYSES

The efficacy analyses will be based on the mITT Population. Baseline for efficacy is defined as the last nonmissing efficacy assessment before the first dose of study treatment. All statistical tests will be 2-sided hypothesis tests performed at the 5% level of significance. All confidence intervals will be 2-sided 95% confidence intervals, unless stated otherwise.

For efficacy analyses in which study center is a factor, a small center will be defined as a center with fewer than 2 participants for at least 1 treatment group in the mITT Population. Small centers will be pooled to form pseudo-centers so that each treatment group includes at least 2 mITT participants within the center. Pooling will be done within each country using the following algorithm:

1. Based on the number of mITT participants, small centers will be ordered from the largest to the smallest, and centers of the same size will be ordered from the largest center number to the smallest center number.
2. The pooling process starts with the largest small center from the top, which will be pooled with the smallest from the bottom until a non-small center is formed.
3. The process will be repeated using the small centers left out after the first pass.

If any centers are left out at the end of the process, they will be pooled with the smallest pseudo-center. If there is more than 1 smallest pseudo-center, the pseudo-center with the smallest center number will be selected. In case that the pseudo center formed by pooling all small centers is still a small center, it will be pooled with the smallest non-small center. If there is more than 1 smallest non-small center, the one with the smallest center number will be selected.

The pseudo-centers will be used for all efficacy analyses when the model is adjusted for study center.

The rater-administered MADRS will be used for the efficacy analyses.

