10.3 ADDITIONAL EFFICACY PARAMETERS

Additional efficacy parameters are as follows:

- Change from baseline in Clinical Global Impressions-Severity (CGI-S) at Day 2 (1 day after first dose), Day 8, Day 9 and Day 15
- MADRS responder status at Day 2 (1 day after first dose), Day 8, Day 9, Day 15 and Day 22
- CGI-S responder status at Day 2 (1 day after first dose), Day 8, Day 9 and Day 15
- MADRS remitter status at Day 2 (1 day after first dose), Day 8, Day 9, Day 15 and Day 22
- Time to first response
- Time to first remission

Analysis of change from baseline in CGI-S score will be performed using a similar MMRM to that used for the key secondary parameter. Multiple comparison procedure will not be applied to the above additional efficacy parameters.

Plots of fitted (least squares) mean values and their standard errors based on the MMRM model for the change from baseline in MADRS total score and in CGI-S score, respectively, will be presented by treatment group and by visit.

CGI-S responder is defined as participants achieving a score of ≤ 2 on the CGI-S of Illness scale.

During the randomized treatment period, 2 types of events for MADRS total score will be defined based on the following criteria:

- Responder: $\geq 50\%$ reduction from baseline MADRS total score
- Remitter: MADRS total score ≤ 10

Rates of responders and remitters will be reported by treatment group for each timepoint (Days 2, 8, 9, 15, and 22 after first dose of randomized treatment). A logistic regression model with LOCF imputation will be used to model the probability of a response or the probability of a remission as a function of a treatment group and baseline MADRS or CGI-S total score. The LOCF approach will be used to impute missing postbaseline values, provided that at least 1 postbaseline assessment is available. Missing values between the baseline and the first nonmissing postbaseline will be imputed with the baseline value. If all the postbaseline values are missing, the baseline value will not be carried forward. Only the total score of a parameter will be imputed using the LOCF approach; individual item scores will not be carried forward. Bar charts for the rates of responders and remitters in MADRS total score will be presented by treatment group and by study day.

Descriptive statistics for the first three additional endpoints and their associated statistical testing results from the MMRM models and logistic regression will be respectively presented by visit.

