The time to onset of first event (i.e. first response or first remission) is defined as the number of days from the first randomized dosing to the first event. The time to onset in days will be calculated for each type of event (first response or first remission) in person level. Participants who do not meet the criteria for respective type of event will be censored at the time of their last MADRS assessment during the treatment period.

For each type of event, the proportion of participants with onset of first events, Kaplan-Meier estimate in terms of the median time to onset of first event, and its 95% CI will be presented for each treatment group. Plots of the Kaplan-Meier estimate of the distribution of the time to onset of events will also be provided for each treatment arm. Log-rank tests comparing the time to onset of event distribution between each AGN-241751 dose and placebo will be conducted.

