14.0 DETERMINATION OF SAMPLE SIZE

The sample size of approximately 25 randomized participants in each of the 4 treatment groups is not based on statistical power consideration due to the lack of information of AGN-241751 for the variability of change from baseline to 1 day after first dose in MADRS total score.

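### Time to first remission is compared by a log-rank test with no baseline adjustment and no between-arm estimate; a supportive baseline-adjusted model should sit beside it

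*SAP*

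**What the plan says.** SAP 10.3 measures days from the first randomized dose to first response (at least a 50% fall from the participant's own baseline MADRS) or first remission (MADRS total of 10 or less). Participants without the event are censored at their last on-treatment MADRS. Each arm gets the proportion with an event, a plot, and the "Kaplan-Meier estimate in terms of the median time to onset of first event, and its 95% CI will be presented for each treatment group". Between arms there is only this: "Log-rank tests comparing the time to onset of event distribution between each AGN-241751 dose and placebo will be conducted". No covariate, stratum or effect measure is named, and Protocol 10.3.1.3.1 says the same.

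Other analyses of the same scale do use baseline. SAP 10.3 models response and remission at each visit by logistic regression "as a function of a treatment group and baseline MADRS or CGI-S total score", and SAP 10.1 and 10.2 put baseline and its interaction with visit into the MMRM.

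On design, Protocol 6.1 criterion 4 reads "Have a minimum score of 26 on the rater-administered MADRS at both Screening (Visit 1) and Visit 2", and no upper limit on the total score is given. SAP 4.0 states: "Participants will be randomized in a ratio of 1:1:1:1 to 1 of 4 treatment groups". Protocol 7.3 states: "All participants will be centrally assigned to randomized study treatment using an IWRS", and no stratification factor is described. SAP 14.0 states: "The sample size of approximately 25 randomized participants in each of the 4 treatment groups is not based on statistical power consideration". SAP 10.0 applies one level throughout: "All statistical tests will be 2-sided hypothesis tests performed at the 5% level of significance".

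**The concern.** Remission is an absolute cut, so a participant who enters with a higher score has further to fall. With small arms and no stated stratification, one arm can by chance start more severe than another, and an unadjusted comparison reads part of that difference as slower remission. The plan guards against this for the MMRM and for the by-visit models of the same events, but not for time to event, and it gives no reason for the difference.

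The log-rank test also yields only a p-value. In a study with no power basis, an estimate with its interval tells the reader more than whether a 5% threshold was crossed. Protocol 3.3 names rapid onset among the expected benefits, and the time-to-event endpoints address onset directly.

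**Working it through.** **1. The plan's own figures.** 4 arms × 25 = 100, which agrees with the stated total. The documents give no power, event rate, hazard ratio, baseline SD or placebo change, so nothing else can be reproduced. Every magnitude below rests on assumed inputs.

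**2. Required fall (documents only).** Entry at 26 needs 26 − 10 = 16 points; entry at 38 needs 38 − 10 = 28.

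**3. Chance of remission by baseline b.** Assume a placebo Day 15 change with mean −12 and SD 9, unrelated to baseline. Then P = Φ((10 − b + 12)/9):
- b = 26: Φ(−4/9) = 33%
- b = 32: Φ(−10/9) = 13%
- b = 38: Φ(−16/9) = 4%

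If the mean change steepens by 0.25 per baseline point around 32, the figures are Φ(−5.5/9) = 27%, 13%, and Φ(−14.5/9) = 5%.

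**4. Size of chance imbalance.** The SE of the difference in mean baseline is SD × √(2/25) = 0.283 × SD. For a baseline SD of 2.8 to 4.8 (after the cut at 26) this is 0.8 to 1.4 points.

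**5. Simulation for remission.** Two arms of 25, with MADRS on Days 2, 8, 9 and 15. Assumed: baseline about 32 truncated at 26; placebo means 24, 22, 21, 19 at those visits; a 5-point drug effect; residual SD 8; no dropout. The slope of the post-baseline score on baseline runs from 0.4 to 1.0. The adjusted analysis is a discrete-time logistic hazard model with baseline MADRS as a covariate. Cells give the percentage of trials significant in favour of the active arm when it starts more than 1 SE more severe / more than 1 SE milder.

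| Dependence on baseline | Log-rank (20,000 trials) | Log-rank (3,000 trials) | Adjusted (same 3,000) |
|---|---|---|---|
| Weak: slope 0.4, SD 2.8 | 37 / 52 | 34.5 / 52.4 | 36.7 / 39.6 |
| Middle: slope 0.7, SD about 3.9 | 27 / 58 | 25.5 / 53.7 | 41.0 / 36.3 |
| Strong: slope 1.0, SD 4.8 | 15 / 61 | 13.1 / 55.3 | 35.6 / 37.7 |

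With residual SD 5, the log-rank gives 43 / 78 (middle) and 23 / 82 (strong).

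Overall power is 36–44% for the log-rank and 39–41% for the adjusted model. Null rejection is 4.7–5.4% for the log-rank and 1–4% for the adjusted model, so the adjusted power is somewhat understated. The two analyses disagree on significance in 7–21% of trials with an effect and in 3–5% without.

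A second simulation used the inputs of step 3 with baseline about 32 (SD 4.5 before the cut at 26) and a 6-point effect. Log-rank power was about 20–23% when the active arm started more than 1 SD of the imbalance more severe and 58–59% when milder; the adjusted figures were 35–40% and 44–45%. Overall power was 36–38% against 42%, with the adjusted likelihood-ratio test slightly liberal at about 6–7%.

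**6. Response.** In the step 5 simulation, log-rank power (more severe / milder) is 54–55 / 50–51% at slope 0.4, 46–49 / 56–59% at slope 0.7 and 34–41 / 61–64% at slope 1.0. The direction reverses at the low slope, and the shift is large only near slope 1.

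**7. Precision of a hazard ratio.** With d events in a pairwise comparison, the SE of the log hazard ratio is about 2/√d, so the 95% limits are the estimate times or divided by exp(1.96 × 2/√d). That factor is 3.5 for d = 10 and 2.0 for d = 30 (d assumed).

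**The case against.** The case for leaving the plan alone is substantial. The log-rank test is valid under randomization and keeps its level. Average power barely moves. These are additional endpoints outside any multiplicity procedure, and the primary and secondary conclusions come from a baseline-adjusted MMRM. A reader worried about imbalance can look at the adjusted by-visit logistic models. Baseline luck is also a minority of the noise. If each point of imbalance moves the log hazard ratio by 0.10 to 0.17, a 1.1-point imbalance moves it by 0.11 to 0.19. Against an SE of 0.37 to 0.63 that is (0.11/0.63)² = 3% to (0.19/0.37)² = 26% of the sampling variance.

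A proportional-hazards model has faults of its own. Part A gives a single dose in the first week and daily dosing in the second, so one hazard ratio averages over unlike periods. With four visit times and few events, test size is only approximate: the Cox model with Breslow ties rejected in 2–3% of null trials, the discrete-time model in 1–4% for remission, and the likelihood-ratio test in about 6–7%.

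All of this stands, and it rules out demoting the log-rank test. It does not remove the gap. The logistic models use LOCF while the time-to-event analysis censors, and they answer a question about each visit rather than about onset. No between-arm time-to-event estimate exists anywhere in the plan.

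**Conclusion.** The point holds as a modest improvement, chiefly for time to first remission. The documents establish three things: the comparison is unadjusted, no between-arm time-to-event effect is planned, and the related analyses of the same scale adjust for baseline. The size is assumption-based. Log-rank power for remission runs from 15–37% to 52–61% according to the direction of a baseline imbalance beyond 1 SE, against roughly 35–45% in both directions after adjustment.

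A reader might infer more, and the documents do not support it:
- **An invalid test or inflated error.** The log-rank keeps its 5% level; the loss is conditional on the imbalance that happens to occur.
- **Strong dependence of remission on baseline as a fact.** No document gives its strength; over the assumed range the effect runs from modest to large.
- **The same problem for response.** Response is scaled to own baseline and shifts materially only when the slope is near 1.
- **No effect size at all.** Per-arm proportions and medians with intervals are planned; only the between-arm contrast is missing.
- **A trial verdict at risk.** No formal conclusion rests on these endpoints.

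The figures apply to about 25 per arm in Part A. Part B plans about 40 per arm and has a separate SAP, so they do not transfer.

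**What to change.** Keep the protocol-specified Kaplan-Meier summaries and log-rank tests. Add to SAP 10.3 a supportive model with treatment (four levels) and baseline MADRS as a continuous covariate: either a discrete-time complementary log-log model over the scheduled visits or a Cox model with exact handling of ties. Report the hazard ratio and 95% CI for each dose versus placebo, chiefly for time to first remission, and for response for consistency. State the tie handling in advance, and say that the hazard ratio averages over the single-dose and daily-dose weeks. Record the addition in SAP 17.0, which now lists no changes.

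The cost is SAP wording and one more model. No new data are needed, since the mITT definition already requires a baseline MADRS. The price is a wide interval when events are few, an approximate test size in small samples, and a summary ratio that relies on proportional hazards.

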11.0 SAFETY ANALYSES

The safety analysis will be performed using the safety population. The safety parameters will include adverse events (AEs), clinical laboratory including, vital signs, electrocardiographic (ECG), C-SSRS, BPRS+, and CADSS parameters. The last nonmissing safety assessment before the first dose of study treatment will be used as the baseline for all analyses of that safety parameter. Continuous variables will be summarized by number of participants and mean, SD, median, Q1 (25 percentile), Q3 (75 percentile), minimum, and maximum values. Categorical variables will be summarized by number and percentage of participants.

11.1 ADVERSE EVENTS

Adverse events will be coded by system organ class and preferred term using the *Medical Dictionary for Regulatory Activities* (MedDRA), version 22.0.

An AE will be considered a treatment-emergent adverse event (TEAE) if the AE began or worsened (increased in severity or became serious) on or after the date of the first dose of study medication. However, an AE that occurs more than 30 days after the last dose of study medication will not be counted as a TEAE. Per case report form instructions, a new AE record will be created with a new AE onset date for any AE that worsens. Therefore TEAEs can simply be identified as those AEs with recorded onset date on or after the date of the first dose of study intervention and within 30 days after the last dose of study intervention.

The number and percentage of participants reporting TEAEs in each treatment group will be summarized overall and weekly. The number and percentage of participants reporting TEAEs in each treatment group will be tabulated by descending percentage in any group, by system organ class and preferred term, and further categorized by severity and causal relationship to the study treatment. If more than 1 AE is coded to the same preferred term for the same patient, the patient will be counted only once for that preferred term using the greatest severity and strictest causality for the summarization by severity and causal relationship.

The total number of TEAEs by system organ class and preferred term; system organ class, preferred term, and severity; system organ class, preferred term, and causal relationship to the study treatment will be summarized by treatment group.

The incidence of common ($\geq 2\%$ of participants in any treatment group) TEAEs will be summarized by preferred term and treatment group and sorted by decreasing frequency for the test treatment highest dose. It will be reported for Safety population overall.

The number and percentage of participants in the Safety Population who have AEs leading to premature discontinuation of the study treatment will be summarized by preferred term and treatment.

The number and percentage of participants who have TESAEs (treatment-emergent serious adverse event) will be summarized by preferred term and treatment group. An AE will be considered a TESAE if it is a TEAE that additionally meets any SAE criteria. Summary tables will be provided for participants with TESAEs and participants with TEAEs leading to discontinuation if 2 or more participants reported such events. Listings of all AEs, SAEs, and AEs leading to discontinuation by participant will be presented.

11.2 CLINICAL LABORATORY PARAMETERS

Descriptive statistics for clinical laboratory values (in SI units) and changes from the baseline values at each assessment time point will be presented by treatment group for the following laboratory parameters, measured at Screening and Visit 6/ET:

Hematology: Absolute and differential white blood cell count, erythrocyte count, hemoglobin, hematocrit, platelet count, and red blood cell indices (mean corpuscular volume, mean corpuscular hemoglobin, and mean corpuscular hemoglobin concentration)

Chemistry: Sodium, potassium, calcium, chloride, bicarbonate, magnesium, gamma glutamyl transferase, phosphate, glucose, blood urea nitrogen, creatinine, creatine phosphokinase, total protein, alkaline phosphatase, albumin, bilirubin (total; direct; indirect), ALT, AST, total cholesterol, low-density lipoprotein, high-density lipoprotein, triglycerides

Urinalysis: Specific gravity, pH, protein, glucose, ketones, and blood
Urine drug screen (UDS): Benzoylecgonine (cocaine), barbiturates, amphetamines, benzodiazepines, cannabinoids, opiates, methadone, phencyclidine

Pregnancy at Screening and Visit 6/ET: Serum β -hCG

The following clinical laboratory levels will be measured at Screening only:

Clinical laboratory screening tests: HbA1c, fasting insulin, TSH, T3, and free T4

Hepatitis screening: HCV antibody, hepatitis-B surface antigen, and hepatitis-B core antibody total will be tested. Reflex hepatitis-B core antibody IgM will be performed for all hepatitis-B core antibody total positive or reactive results. Positive test results will be sent for confirmation testing.

Clinical laboratory test values will be considered potentially clinically significant (PCS) if they meet either the lower-limit or higher-limit PCS criteria listed in [Table 11-1](#). The number and percentage of participants who have PCS postbaseline clinical laboratory values will be tabulated by treatment group. The percentages will be calculated relative to the number of participants with available non-PCS baseline values and at least 1 postbaseline assessment. The numerator will be the total number of participants with available non-PCS baseline value and at least one postbaseline assessment. A supportive tabular display of participants with PCS postbaseline values will be provided, including the PID number, baseline and all postbaseline (including non-PCS) values.

In addition, a tabular display showing all AEs that occurred in participants who had PCS postbaseline clinical laboratory values will be provided.

Table 11-1 Criteria for Potentially Clinically Significant Clinical Laboratory Tests

Laboratory Parameter	SI Unit	Conversion Factor^a	Traditional Unit	PCS Criteria^b Low Values	PCS Criteria^b High Values
Hematology					
Hemoglobin	g/L	0.1	g/dL	< 0.9 × LLN	—
Hematocrit	volume fraction	100	%	< 0.9 × LLN	—
Eosinophils	%	1	%	—	> 10
Neutrophils	%	1	%	< 30	> 90
Basophils	%	1	%	—	> 6
Monocytes	%	1	%	—	> 20
Lymphocytes	%	1	%	< 10	> 60
Abs Neutrophils (ANC)	10 ⁹ /L	1	1000/µL	< 1.0	—
Platelet count	10 ⁹ /L	1	1000/µL	≤ 75	≥ 700
White cell count	10 ⁹ /L	1	1000/µL	≤ 2.5	≥ 15
Chemistry					
Albumin	g/L	0.1	g/dL	< 0.9 × LLN	> 1.1 × ULN
Alkaline phosphatase	U/L	1	U/L	—	≥ 3 × ULN
ALT (SGPT)	U/L	1	U/L	—	≥ 3 × ULN
AST (SGOT)	U/L	1	U/L	—	≥ 3 × ULN
Gamma-glutamyl transferase (GGT)	U/L	1	U/L	—	≥ 3 × ULN
Blood urea nitrogen (BUN)	mmol/L	2.8011	mg/dL	—	> 1.2 × ULN
Calcium	mmol/L	4.008	mg/dL	< 0.9 × LLN	> 1.1 × ULN
Chloride	mmol/L	1	mg/dL	< 0.9 × LLN	> 1.1 × ULN
Cholesterol	mmol/L	38.6698	mg/dL	—	> 1.3 × ULN
High-density lipoprotein (HDL) cholesterol	mmol/L	39	mg/dL	< 0.8 × LLN	—

Laboratory Parameter	SI Unit	Conversion Factor^a	Traditional Unit	PCS Criteria^b Low Values	PCS Criteria^b High Values
Low-density lipoprotein (LDL) cholesterol	mmol/L	39	mg/dL	—	> 1.2 × ULN
CPK	u/L	1	mg/dL	—	> 1.5 × ULN
Creatinine	µmol/L	0.0113	mg/dL	—	> 1.3 × ULN
Glucose, fasting	mmol/L	18	mg/dL	< 0.8 × LLN	> 1.2 × ULN
Magnesium	mmol/L	2	mEq/L	< 0.9 × LLN	> 1.1 × ULN
Potassium	mmol/L	1	mEq/L	< 0.9 × LLN	> 1.1 × ULN
Sodium	mmol/L	1	mEq/L	< 0.9 × LLN	> 1.1 × ULN
Total bilirubin	µmol/L	0.0585	mg/dL	—	> 1.5 × ULN
Total protein	g/L	—	—	< 0.9 × LLN	> 1.1 × ULN
Triglycerides, fasting	mmol/L	88.6	mg/dL	—	> 1.2 × ULN
Urinalysis					
Protein	—	—	—	—	At least 2 +
Glucose	—	—	—	—	At least 2 +
Blood	—	—	—	—	At least 2 +

a Conversion factor from SI units to traditional units.

b Criteria refer to SI units.

Blood urea nitrogen or Urea are the same parameters, and Uric acid or Urate are the same parameters.

LLN = lower limit of normal; PCS = potentially clinically significant; SI = *Le Système International d'Unités* (International System of Units); ULN = upper limit of normal of laboratory reference range.

In addition, descriptive statistics for clinical laboratory values and changes from the baseline values in conventional units at each assessment time point will be presented for selected clinical laboratory parameters listed in [Table 11-2](#).

Table 11-2 Selected Parameters Reported in Conventional Units

Number	Laboratory Parameter	Conventional Unit
1	Alanine Aminotransferase (SGPT)	U/L
2	Albumin	G/dL
3	Alkaline Phosphatase	U/L
4	Aspartate Aminotransferase (SGOT)	U/L
5	Bilirubin, Direct (Conjugated)	mg/dL
6	Bilirubin, Indirect (Unconjugated)	mg/dL
7	Bilirubin, Total	mg/dL
8	Blood Urea Nitrogen	mg/dL
9	Calcium	mg/dL
10	Cholesterol, HDL	mg/dL
11	Cholesterol, LDL	mg/dL
12	Cholesterol, LDL direct and calculated (combined) (may be reported with #11)	mg/dL
13	Cholesterol, Total	mg/dL
14	Creatine Kinase	U/L

Number	Laboratory Parameter	Conventional Unit
15	Creatinine	mg/dL
16	Glucose	mg/dL
17	Insulin	uIU/mL
18	Triglycerides	mg/dL
19	Uric Acid	mg/dL
20	Hemoglobin	G/dL

